2. PROTOCOL SYNOPSIS

TITLE	Preventing Cholestasis in Premature Infants Using SMOFLipid®					
OBJECTIVES	
Primary Objective
 
 To compare a mixed parenteral lipid emulsion containing fish oil (SMOFLipid®) with a soybean oil based lipid emulsion (Intralipid®) for its effect on the occurrence of parenteral nutrition associated cholestasis in extremely low birth weight infants 
Secondary Objectives
 
 To assess the impact of SMOFLipid® on the long term neurocognitive development of extreme low birth weight infants at 12 and 24 months of corrected age 					
DESIGN / PHASE	Prospective, randomized, double-blind, phase IV study.					
STUDY PLANNED DURATION	First patient First visit	1st month	Last patient First visit	36 month s	Last patient Last visit	62 months
CENTER(S) / COUNTRY(IES)	Single center, Austria (Medical University Vienna, Austria; Department of Neonatology, Pediatric Intensive Care and Neuropediatrics, University Children's Hospital,)					
PATIENTS / GROUPS	
200 patients in 2 groups 100 patients per group Block randomization ratio 1:1, stratification by sex and weight (in two groups: < 750 gram vs. ≥750 gram).
 
In case of twins, randomization will be applied to the firstborn; the twin will be assigned to the other treatment group. Triplets or higher will be excluded.
					
INCLUSION CRITERIA	
 Infants born with a birth weight ≤ 1000 Gram (= extreme low birth weight infants) Admission to the neonatal ward in the first 24 hours of life Informed consent obtained and randomized on study drug the first 5 days of life 					
EXCLUSION CRITERIA	
 Triplets or higher Conjugated bilirubin > 1.5 mg/dl before inclusion to the study Conditions associated with cholestasis independent of parenteral nutrition: 
 Inborn errors of metabolism Viral Infections (cytomegaly virus, HIV, Hepatitis B, C) Immune mediated hemolytic disease (e.g. Rhesus incompatibility) Cystic fibrosis Primary cholestatic diseases of the liver For Neurodevelopmental outcome in follow up phase: Congenital neurological malformations and chromosomal aberrations 					

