STATISTICAL METHODOLOGY	
Primary Endpoint PNAC (definition see efficacy endpoint)
 
Null and alternative hypotheses: H₀ : The percentage of PNAC in group 1 (investigational drug) equals group 2 (comparative drug) H₁: The percentage of PNAC in group 1 (investigational drug) does not equal group 2 (comparative drug)
 
Sample size calculation A sample size estimation using a χ^2-test indicated that 200 infants (100/group) are required to detect a 15% difference (10% in group 1 vs. 25% in group 2) with a power of 80% and a two-sided significance level of 0.05. The estimated drop out rate is 22%. Therefore, a sample size of 122 patients per group is planned. For sample size estimation, data were assumed to be independent.
 
Statistical methodology Main analysis set(s) A χ^2-test will be used for analysis of the primary outcome PNAC. Additionally, the effect of treatment and other relevant influence factors (i. e. duration of parenteral nutrition, birth weight, necrotizing enterocolitis) on the primary endpoint will be analyzed using a logistic regression model with

	
stepwise selection. In case of twins, the analysis will be carried out 1) as mentioned above, but only including the firstborn and 2) by calculating a generalized linear model with mother as random factor.
 
Other endpoints
 
Bailey Scales of Infant Development III at 12 and 24 months: Differences in the scores of psychomotor development and neurocognitive development, respectively, between the groups will be analyzed by repeated measures ANOVAs, also accounting for confounder factors (e.g. birth weight, ...). In case of twins, the analysis will be carried out 1) as mention above, but only including the firstborn and 2) by calculating a mixed model with mother and child as random factor. In case of too many drop outs, descriptive statistics will be carried out.
 
For Gross Motor function measurements at 12 and 24 months, descriptive statistics will be conducted.

--	--

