7. STUDY DESIGN

7.1 Study population

7.1.1 Subject population

Population: Extreme low birth weight (ELBW) infants

Recruitment: About 90 ELBW infants are admitted to our unit each year in the first 24 hours of life.

We expect to recruit 90 % (81 patients/a year) to the study.

Drop Outs: Based on a mortality of 22% in 2010 ([name], unpublished data) and a conservative calculation, we expect 18/81 patients to drop out, leaving 63 patients a year for analysis of the primary outcome. We do not expect any other reasons for drop out.

Losses to follow up: 63 patients are expected to be discharged from hospital each year. Based on a follow up rate of 60% after discharge in 2009 ([name], unpublished data), we expect about 38/63 patients to be available for analysis of the secondary outcome each year. In the end we expect to lose 80/200 patients to follow up.

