7.1.5 Withdrawal and replacement of subjects

Criteria for withdrawal

Premature discontinuation from the study is to be understood when the subject did not undergo End of Study (EOS) examination and / or all pivotal assessments during the study.

Subjects must be withdrawn under the following circumstances:

- at their parent's request at any time
- if the investigator feels it would not be in the best interest of the subject to continue
- if the subject violates conditions laid out in the consent form / information sheet or disregards instructions by the study personal
- if the subject is transferred to another hospital before parenteral nutrition is discontinued
- if the study drug was not provided < 80% of time as planned per protocol
- If an exclusion criterion is met, after inclusion to the study (except neurological malformation and chromosomal aberration which only leads to withdrawal from follow up analysis except screening for adverse events)
- death before day of life 28

In all cases, the reason why subjects are withdrawn must be recorded in detail in the CRF and in the subject's medical records. Should the study be discontinued prematurely, all study materials (complete, partially completed and empty CRFs) will be retained.

Follow-up of patients withdrawn from the study

In case of premature discontinuation after study drug intake, the investigations scheduled for the EOS visit will be performed 7 +/-4 days after study drug discontinuation. The subjects will be advised that participation in these investigations is voluntary. Furthermore, they may request that from the time point of withdrawal no more data will be recorded and that all biological samples collected in the course of the study will be destroyed.

Replacement policy

Patients withdrawn from the study < 28 days (outcome cannot be calculated) will be replaced and the next free subject number will be allocated. Drops outs will be included in the sample size. If patients are withdrawn from the study and the outcome can be calculated, (more than two blood samples taken), they will be considered in the intention to treat analysis (see chapter 10)

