11.2 Sample size considerations

Data investigating the incidence of PNAC in our unit showed an incidence of 25 % from 2007-9 (unpublished data). We considered a difference of 15% between the groups (incidence of PNAC: 25% for Intralipid and 10% for SMOFLipid, respectively) as a clinically relevant effect. A sample size estimation based on a χ^2 -test indicated that 200 infants (100/group) are required to detect a difference of 15% between the groups with a power of 80% and a significance level of 0.05. The estimated drop out rate is 22%. Therefore, a sample size of 122 patients per group is planned. For sample size estimation, data were assumed to be independent.

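### The plan gives two different patient numbers (200 and 244) and a replacement rule that is not reconciled with the 22% drop-out allowance, so it is unclear when recruitment stops

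*Combined protocol and SAP*

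**What the plan says.** Four places bear on the number to randomise.

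- **Synopsis, Patients / Groups row:** "200 patients in 2 groups 100 patients per group Block randomization ratio 1:1". The figure 244 does not appear in this row.
- **Section 11.2, and the synopsis statistics row in nearly the same words:** "200 infants (100/group) are required to detect a difference of 15% between the groups", followed in 11.2 by "The estimated drop out rate is 22%. Therefore, a sample size of 122 patients per group is planned". That is 244 in total.
- **Section 7.1.1:** the 22% is the unit's mortality in 2010. It is applied as 18 losses among 81 recruits a year, leaving 63 for the primary analysis, and the section adds "We do not expect any other reasons for drop out".
- **Section 7.1.5:** death before day of life 28 is a withdrawal criterion. Infants withdrawn before 28 days, described as having no calculable outcome, "will be replaced and the next free subject number will be allocated. Drops outs will be included in the sample size".

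The parameter list in section 8.5.4 also classes death before 28 days as drop-out. No section says whether recruitment ends at a number randomised or at a number evaluable.

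**The concern.** Inflating the sample size and replacing lost patients are two ways of covering the same loss. Here an infant who dies before day 28 falls under both: the death belongs to the mortality behind the 22%, and it also triggers replacement. The sentence after the replacement rule says that drop-outs are already counted in the sample size, without saying which sample size or how that fits with replacement. The synopsis row then sets a different number beside the allocation ratio.

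The staff running recruitment need one number and one stopping rule. The readings that the text allows differ in power, in calendar time and in how many extremely low birth weight infants are randomised.

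**Working it through.** **Inputs.** PNAC 25% against 10% (11.2: "incidence of PNAC: 25% for Intralipid and 10% for SMOFLipid, respectively"); chi-square test "with a power of 80% and a two-sided significance level of 0.05" (synopsis); 1:1 allocation; loss 22% (11.2); recruitment 81 a year (7.1.1); last patient's first visit at month 36 (synopsis, planned duration).

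**The plan's own figures.** With mean proportion 0.175 and difference 0.15,

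n per group = [1.960 × √(2 × 0.175 × 0.825) + 0.842 × √(0.25 × 0.75 + 0.10 × 0.90)]² / 0.15² = (1.053 + 0.443)² / 0.0225 ≈ 99.5, so 100.

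This reproduces the 100 per group (power 80.2%). The 122 is reproduced as 100 × 1.22. Dividing by the retained fraction gives 100 / 0.78 = 128.2, so 129 per group. This matters below, because 244 does not yield 200 evaluable infants at 22% loss: 244 × 0.78 = 190.3. Section 7.1.1 agrees, since 63 a year over three years is 189.

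**Each reading at 22% loss.** As in 7.1.1, the whole 22% is treated as lost to the primary analysis. Evaluable = randomised × 0.78, or randomised = evaluable / 0.78; months = randomised / 81 × 12. Power uses the same formula at the evaluable number per arm.

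| Reading | Randomised | Evaluable | Power | Months |
|---|---|---|---|---|
| Stop at 200 randomised | 200 | 156 (78 per arm) | about 70% | 29.6 |
| 244 in all, no replacement | 244 | about 190 (95 per arm) | about 78% | 36.1 |
| Replace until 200 evaluable | 200 / 0.78 = 256.4, so 257 | 200 (100 per arm) | about 80% | 38.1 |
| Replace on top of 244 (upper bound) | 244 / 0.78 = 312.8, so 313 | 244 (122 per arm) | about 87% | 46.4 |

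**Why the last row is only a bound.** It assumes that every loss falls before day 28 and so triggers replacement. Section 7.1.1 gives no time window for the mortality figure. If a fraction f of the 22% falls before day 28, the total is 244 / (1 − 0.22f): 244 at f = 0, about 274 at f = 0.5 (244 / 0.89), 313 at f = 1.

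**Which reading fits the timetable.** Three years at 81 a year gives 243, which matches 244 randomised by month 36. Section 7.1.1 also puts expected follow-up losses at 80 of 200, so it uses 200 as a number remaining after drop-out. Both point to 244 randomised with 200 meant as the evaluable number, although 244 falls about 10 short of that at 22% loss.

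**The case against.** The strongest reply is that the text can be reconciled. On that view 200 evaluable infants are required, 244 are randomised, and the 44 extra places are where the replacements come from; this is what the sentence about including drop-outs means. The synopsis itself gives 122 per group in its statistics row, so the 200 in the patients row is a labelling slip. This is probably what was intended, and it fits the recruitment arithmetic. It remains an inference: the protocol nowhere states it, and under it the replacement rule adds nothing to a fixed total of 244.

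Two further replies stand. First, a reader might infer that recruitment would run to about 313, some 69 infants and 10 months beyond plan. The documents do not support that as an expected figure: it needs 244 to be an evaluable target, which no section says, and all the mortality to fall before day 28. The only evaluable target in the plan is 200, and replacing up to that number costs 257 − 244 = 13 infants and about 2 months. Second, a reader might infer that any replacement beyond 244 randomises infants the design does not need. That is not so either. The 244 leaves room for 44 losses, but 22% of 244 is about 54, so the first replacements would serve to reach 200. Replacement would also cover early withdrawals for reasons other than death, such as parental request or transfer, for which the 22% allows nothing.

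Nor do the documents show bias from the replacement rule. Its trigger is early withdrawal without a calculable outcome, not PNAC; no interim analysis is planned, and the prescribing doctors are blinded, although the nurses are not.

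**Conclusion.** The point holds as an inconsistency in the number to randomise together with an unreconciled replacement rule. The documents state 200 and 244, and the number at which recruitment stops under replacement is undefined. The most coherent reading is 244 randomised in all, but it has to be inferred.

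The consequence is moderate. Among the readings that rest on a stated figure, expected power runs from about 70% (200 randomised) through about 78% (244 without replacement) to about 80% (about 257, replacing until 200 are evaluable), and recruitment from about 30 to 38 months. The figure of about 313 is a ceiling and should not be quoted as the likely total. These results assume the plan's event rates, 81 recruits a year, independent infants as the plan assumes, and the full 22% lost to the primary analysis. If infants who die later have a calculable outcome and are analysed, the evaluable numbers would be somewhat higher.

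**What to change.** State one total and one stopping rule, and use them in the synopsis patients row, the synopsis statistics row, 7.1.5 and 11.2.

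The cheapest version is:

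- recruitment ends when 244 infants have been randomised, whatever the number of withdrawals;
- the replacement sentence in 7.1.5 is deleted, or reworded to say that replacements come from within the 244;
- the synopsis patients row is corrected to 244, 122 per group;
- 11.2 and the synopsis statistics row keep 200 as the number giving 80% power, but state that 244 randomised at 22% loss is expected to leave about 190 evaluable, with about 78% power.

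This changes wording only, adds no infants and fits the planned 36 months. The cost is a slightly lower stated power, and losses beyond 22% are not topped up.

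If the sponsor wants to keep 200 evaluable and 80% power, the alternatives are a fixed total of 258 (129 per group) without replacement, or recruitment until 200 are evaluable, expected at about 257 randomised. Either moves the last patient's first visit from month 36 to about month 38, and the study periods in the synopsis would have to follow.

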7.1.6 Premature termination of the study

The sponsor has the right to close this study at any time. The IEC and the competent regulatory authority must be informed within 15 days of early termination.

The trial or single dose steps will be terminated prematurely in the following cases:

- If adverse events occur which are so serious that the risk-benefit ratio is not acceptable.
- If the number of dropouts is so high that proper completion of the trial cannot realistically be expected.

8. METHODOLOGY

8.1 Study medication

Active agent and characteristics:

Investigational Product

Trade name of the agent:	SMOFLipid 200 mg/ml Emulsion zur Infusion
Manufacturer:	Fresenius Kabi Austria GmbH
Drug supply:	Fresenius Kabi Austria GmbH
Storage Instructions:	Do not freeze, do not store > 25° Celsius, protect from light
Route of administration:	Intravenous

Comparator

Trade name of the agent:	Intralipid 20% - Emulsion zur Infusion
Manufacturer:	Fresenius Kabi Austria GmbH
Drug supply:	Fresenius Kabi Austria GmbH
Storage Instructions:	Do not freeze, do not store > 25° Celsius, protect from light
Route of administration:	Intravenous

8.1.1 Dosage and administration

Initial dose:	1 g/kg/d (= 5 ml/kg/d)
Maintenance dose:	3 g/kg/d (=15 ml/kg/d)
Route of administration:	Intravenous
Duration:	As long as parenteral nutrition is needed

8.1.2 Study-drug up- and down titration

According to a stepwise increase or reduction of enteral feedings a proportional increase or reduction of parenteral nutrition will be performed including a reduction of the study drug / comparator. The study drug/comparator will be finished as soon as full enteral feeds are reached and PN is stopped (at 140-160 ml/kg/d of total fluid volume depending on the fluid needs of the infant).

8.1.3 Study drug interruption or discontinuation

The investigator must temporarily interrupt or permanently discontinue the study drug if continued administration of the study drug is believed to be contrary to the best interests of the patient. The interruption or premature discontinuation of study drug might be triggered by an AE, a diagnostic or therapeutic procedure, an abnormal assessment (e.g., laboratory abnormalities), or for administrative reasons, in particular withdrawal of the patient's consent.

Hypertriglyceridemia: The study drug will be interrupted for 24 hours at triglyceride levels > 400 mg/dl or down titrated at triglyceride levels of 251-400 mg/dl. Control measurements of triglyceride levels will be performed in the next 24-72 hours to control for successful normalization of triglyceride levels under parenteral nutrition.

The reason for study drug interruption or premature permanent discontinuation must be documented in the CRF.

8.1.4 Study drug premature permanent discontinuation

Study drug premature permanent discontinuation due to an adverse event

If the reason for premature permanent discontinuation of study treatment is an AE, the patient should have a "Premature End of Study (EOS)" visit with all the assessments performed before the study drug discontinuation, whenever possible.

Study drug premature permanent discontinuation due to another reason than adverse event

If the reason for premature permanent discontinuation of study treatment is not an AE, the patient should be withdrawn from the study (withdrawal of consent) and have the end of study (EOS) visit with all the assessments performed before the study drug discontinuation, whenever possible.

8.1.5 Study-drug delivery & drug storage conditions

The study drug will be delivered from the supplying company to the investigators and stored at room temperature under controlled conditions (22°C +/- 3°C) in a locked room. A min/max thermometer will be used to control for temperature in the storage room. Full documentation of delivery, storage and disposition will be maintained.

[figure not shown]
8.1.6 Study drug packaging and labeling

The study drugs are delivered in sterile glass containers of 100 ml by the manufacturer and will be re-labelled at the study site as described in section 8.3. Storage is described in section 8.1.5. For application to study subjects, the study drugs will be brought to the neonatal wards by a member of the blinding team. For IV application, the study drugs will be transferred from the re-labelled commercial containers to perfusor syringes connected to perfusor lines suitable for IV application. Perfusor syringes will be labelled (see sample labels 1 and 2 below). Preparation for IV application will be done in a laminar air hood under sterile conditions by trained intensive care nurses, forming part of the blinding team.

Sample Label Number 1

Sample Label Number 2

8.1.7 IMP administration & handling

The IMP or comparator must not be frozen or stored > 25° C, application is performed in light protected perfusor syringes and perfusor lines. Application may be performed IV via central and peripheral venous catheters. The IMP or comparator must not be mixed with any other drug besides the commercially available vitamin solutions "Soluvit N" and "Vitalipid" (Fresenius Kabi Austria GmbH).

8.1.8 Drug Accountability

Drug Accountability will be recorded at on-going basis on paper form/source data, Drug dispensing have to be entered into the CRF. Furthermore the correct intake of IMP or any variations concerning that will be recorded in the CRF at each visit during treatment period

8.1.9 Procedures to assess subjects compliance

Whether the IMP or comparator where administered correctly will be followed from the documentation in the electronic patient documentary system used at the neonatal ICU.

8.1.10 Concomitant medication

The well-being of the patient has the first priority, and modifications of concomitant treatment during the trial are allowed as necessary. They should be documented in the patient's records.

In case of of cholestasis (i.e. conjugated bilirubin two times > 1.5 mg/dl),

Ursodeoxycolic acid at 20-30 mg/kg/day is the treatment of choice.

Omegaven® is allowed as add on at 1g/kg/d, if conj. bilirubin > 6 mg/dl,

8.2 Randomization and stratification

On day 0, patients are randomized to one of the two study groups and the study medication is provided. Study subjects will be block randomized (ratio 1:1) and stratified according to sex and birth weight (in two groups: < 750 gram vs. ≥ 750 gram) using an online randomization programme provided by the Center for Medical Statistics, Informatics, and Intelligent Systems of the Medical University of Vienna. In case of twins, randomization will be applied to the firstborn; the twin will be assigned to the other treatment group.

8.3 Blinding

Blinding of subjects, investigators and outcome assessors will be performed as follows:

First re-labelling of the study drug containers (see sample label 1 and 2 below) will be performed by two members of the blinding team not involved in the collection of data, treatment of study subjects or preparation of the study drugs for IV application. The study drugs are kept in glass containers of 100 ml and will be re-labelled with samples as indicated (see sample label 1 and 2 below) and stored as described (section 8.1.5).

Second, for delivery to study subjects the study drugs will be brought to the wards by a member of the blinding team, where the preparation for IV application will be done in a laminar air hood by a member of the blinding team as described in section 8.1.7. As intensive care nurses involved in caretaking of the patients form part of the blinding team, nursing caregivers are not blinded. Medical doctors prescribing the daily amounts of the IMP remain blinded.

Sample Label Number 1

Sample Label Number 2:

8.3.1 Emergency procedure for unblinding

If unblinding of a study participant is required due to an emergency, the code can be broken by the Investigator. Code breaking will be fully documented.

8.3.2 Unblinding at the end of the study.

Codes will be broken after data analysis of the primary outcome, this is after the last patient has finished active phase. Investigators involved in assessment of data in the follow up phase (secondary outcome neurodevelopment) will remain blinded.

